### **Change from baseline in Karolinska Sleepiness Scale on Days 7, 14, and 21**

KSS is recorded on the 'Karolinska Sleepiness Scale' eDiary page at each scheduled timepoint. Change from baseline is calculated as:

- KSS at Scheduled Timepoint – KSS at Day 0

#### **EQ-5D-5L**

Health-related quality of life is recorded on the 'EQ-5D-5L Quality of Life Questionnaire' eDiary page.

The EQ-5D is a standardized instrument for assessing health-related QoL, which provides a simple descriptive profile and a single index value for health status in a variety of health conditions. The EQ-5D includes single item measures of five health dimensions: mobility, self-care, usual activities, pain/discomfort, and anxiety/depression.

The EQ-5D-5L includes five levels of severity (i.e., no problems, slight problems, moderate problems, severe problems, and extreme problems) for each of the five EQ-5D dimensions. These levels are scored from 1=no problems to 5= extreme problems. (EuroQol Research Foundation, 2019).

#### **EQ-5D-5L Health State**

The scores (1-5) for the five dimensions are concatenated into a 5-digit code (in the order mobility, self-care, usual activities, pain/discomfort, and anxiety/depression) that describes the patient's health state.

#### **EQ-5D-5L Index**

From the EQ-5D-5L health state the EQ-5D-5L index values are calculated based on the Crosswalk Value Set for the US. If one of the dimensions has a missing score, the EQ-5D-5L index value is derived as missing.

EQ-5D-5L index values are used for the following endpoint:

- Change from baseline in Health-related quality of life, EQ-5D-5L, on Days 7, 14, and 21.

#### **7.4.7.3 Exploratory Variables**

##### **Elapsed time from Voltaren Gel use to achieving time to meaningful pain relief to end of study**

Date of meaningful pain relief is defined as the earliest date where:

- The answer to "Did you use yesterday the Voltaren Gel as per label and leaflet instructions?" is "No"  
AND
- The answer to "If No, please specify the reason:" is "No pain anymore"

On the 'Study Product Use' eDiary page.

The time to event is derived in days as:

- Date of event/censoring – date of First Treatment Administration +1

Date of First Treatment Administration is derived as explained in section 7.1.

For patients who complete or discontinue the study without event occurrence, the patients are considered "censored" and the date of censoring is the date of study discontinuation recorded on the 'Study Termination' eCRF page.

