Safety	
Number and percent of study subjects reporting AEs or serious AEs (SAEs) while on treatment.
 
 
• Treatment Related.
 
• Non-Treatment Related.
 

Statistical Methods and Planned Analyses	
For the primary objective, a Mixed Model with Repeated Measures (MMRM) will be used to analyse the change from baseline in MVPA average minutes as the response variable. Subject will be included as a random effect. Average minutes of MVPA over Week 1 will be calculated over all non-missing days between study day 1 (product usage) through 7, inclusive. Average minutes of MVPA over Week 2 will be calculated over all non-missing days between study day 8 through 14, inclusive. Average minutes of MVPA over Week 3 will be calculated over all non-missing days between study day 15 through 21, inclusive. Any days beyond day 23 will be excluded from all summaries and analyses and will only be present in listed data.
 
For the secondary objective, functional mobility as measured through wearables and PRO, pain intensity assessed through NRS (daily assessment), activity-related pain and stiffness as measured in the (Likert Scale) WOMAC subscales for composite pain and composite stiffness will be analysed in the same manner as the primary objective.
 
For the exploratory endpoints, correlations between pain relief, mobility, and quality of life indices will be measured throughout the trial. Additionally, the use of concomitant medications and any changes in use of pain relief medications will be recorded throughout the trial.
 
Time to pain relief will be evaluated using Kaplan-Meier curves of QoL factors. The median time to resolution of symptoms based on the Kaplan-Meier curve will be presented as well.

---	---

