To evaluate the effects of Voltaren Gel on correlates of quality of life	Change from baseline in on Days 7, 14, and 21 
 
• Sleep/alertness: Karolinska Sleepiness Scale assessed 1x/day.
 
• Health-related quality of life: EQ-5D-5L
 

Safety	
To monitor any record adverse events (AEs) during study period.	Number and percent of study subjects reporting AEs or serious AEs (SAEs) while on treatment. 
 
• Treatment Related.
 
• Non-Treatment Related.
 

Exploratory	
To explore the link between Voltaren usage, level of pain relief and functional mobility/quality of life	Correlations between Voltaren usage, pain relief and mobility and quality of life indices throughout the trial.
To evaluate time-to meaningful pain relief after Voltaren Gel use	Elapsed time from Voltaren Gel use to achieving time to meaningful pain relief to end of study.

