## **9.2 Study Period**

### **9.2.1 Baseline Period**

The number of days each subject will actively engage with the study will be up to 28 days including baseline ([See Appendix](#)).

Study subjects who fulfil criteria and deemed suitable by the investigator for participation will be provided with the Actigraph wearable device which will measure aspects of functional mobility during the baseline period. The baseline period will last between 3 (minimum) and 7 days (maximum), to collect enough information on both subjective and objective aspects of mobility and sleep quality. End of baseline period will be considered day 0.

The baseline period will be variable and will depend on study subjects reaching  $\geq 40$  mm  $\leq 70$  mm of self-reported pain on the pain intensity visual analogue scale (VAS). Once the subject reaches any value at this level on the VAS scale, even for a single observation, the baseline period will be terminated, and study phase can commence.

At the end of the baseline period, the site staff will dispense the study product to the subject to take home and use throughout the study period as per label instructions. Before they start using the product, study subjects will complete the questionnaires to collect information on their baseline levels of quality of life and subjective perceptions of mobility and exercise capacity.

All medications taken during the 60 days prior to the screening visit and throughout the trial (other than study medication) will be recorded on the eCRF.

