### **13.3.4 Exploratory Analysis(es)**

For the exploratory endpoints, correlations between pain relief, mobility, and quality of life indices will be measured throughout the trial. Additionally, the use of concomitant medications and any changes in use of pain relief medications will be recorded throughout the trial.

Time-to-pain relief will also be measured after use of the test product; this will be measured as the elapsed time from test product use to achieving sufficient pain relief to stop using the product and will be evaluated using Kaplan-Meier curves.

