### Date of Last Study Treatment Administration

Date of last study treatment administration is defined as:

- “Date of last application of study drug” as recorded in the ‘Study Termination’ eCRF page.).

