## 7.4 Analysis Variables

### 7.4.1 Disposition

Subject disposition data are collected on the 'Study Termination' eCRF page. Subjects are recorded as "Completed", "Screening failure", or "Early withdrawal". The date of the disposition event, date of last application of study drug and, if applicable, the date of death is recorded.

If applicable, the primary reason for discontinuation may include any of the following:

- Adverse Event (with a drop down to specify the AE number);
- Death;
- Inclusion not met/ Exclusion criteria met;
- Lack of efficacy;
- Lost to follow-up;
- Non-compliance with study drug;
- Occurrence of pregnancy;
- Physician's decision;
- Protocol violation;
- Withdrawal of consent;
- Withdrawal due to no pain;
- Other (with a free text to specify).

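### Exploratory time to meaningful pain relief: the diary's one-day lag is removed from first use but not from the event, and withdrawal for no pain without a diary entry is censored

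*SAP*

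**What the plan says.** Both ends of the time interval come from one item on the Study Product Use eDiary page, which asks whether the gel was used on the previous day.

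- **Start.** SAP 7.1 takes the earliest diary date with a positive answer and subtracts one day.
- **Event.** SAP 7.4.7.3: "Date of meaningful pain relief is defined as the earliest date where" the answer is negative and the reason given is that there is no pain any more. Nothing is subtracted.
- **Time.** SAP 7.4.7.3 takes the event or censoring date minus the first-treatment date, plus 1.
- **Censoring.** SAP 7.4.7.3: "For patients who complete or discontinue the study without event occurrence, the patients are considered" censored, at the discontinuation date on the Study Termination page. The reason for termination plays no part.
- **Termination page.** SAP 7.4.1 lists "Withdrawal due to no pain" among the primary reasons for discontinuation. SAP 7.1 takes the last treatment date from "Date of last application of study drug" on the same page.
- **Protocol.** Section 13.3.4 measures the time to "achieving sufficient pain relief to stop using the product". Table 3-1 words the endpoint as "Elapsed time from Voltaren Gel use to achieving time to meaningful pain relief to end of study", and the Statistical Methods part of the Protocol Summary promises the "median time to resolution of symptoms based on the Kaplan-Meier curve".

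SAP 8.2.4 and 10.6.3 report the Kaplan-Meier median with its 95% CI and both quartiles, in days, for the mITT population.

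**The concern.** There are two separate gaps in the derivation.

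1. The subtraction in SAP 7.1 recognises that a diary entry describes the day before. The event rule uses the same question and does not make that correction. The clock then starts on a day of use and stops on a day of reporting. With roughly 21 treatment days and results in whole days, one day is visible in every reported quantile.
2. Leaving the study because pain has gone is the event that Protocol 13.3.4 describes. If it is recorded only on the termination page, SAP 7.4.7.3 turns it into a censored observation. That censoring is informative: the subject leaves because the outcome was reached. It lowers the curve and can leave a quartile unreached.

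The analysis is single-arm and descriptive, with no test attached, so the stake is the accuracy of one exploratory table and figure.

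**Working it through.** The documents give no figure for this endpoint, so there is none to reproduce. The inputs are the date rules in SAP 7.1 and 7.4.7.3.

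**Step 1: the date shift.** Let f be the first day of use and k the first day of non-use because pain has gone. The diary reports these on f + 1 and k + 1.

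- First treatment date (SAP 7.1): (f + 1) − 1 = f.
- Event date (SAP 7.4.7.3, read as the diary entry date): k + 1.
- Time as written: (k + 1) − f + 1 = k − f + 2.
- Time with the 7.1 convention at both ends: k − f + 1.

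| f | k | As written | Same convention |
|---|---|---|---|
| 1 | 2 | 3 | 2 |
| 1 | 7 | 8 | 7 |
| 1 | 14 | 15 | 14 |
| 1 | 20 | 21 | 20 |
| 0 | 7 | 9 | 8 |
| 3 | 7 | 6 | 5 |

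The difference is always one day. Censoring times use an actual date and carry no diary lag.

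The rule also does not require the event to follow first use. A qualifying entry on Day 2 with first use on Day 3 gives 2 − 3 + 1 = 0. This is unlikely, because Protocol 9.2.1 starts treatment only after pain has reached the entry range ("Once the subject reaches any value at this level on the VAS scale, even for a single observation").

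**Step 2: how a known event can be censored.** Let L be the last day of use, so k = L + 1. Protocol 9.2.3 allows the study to end on L + 1 when a subject stops early. The diary on L + 1 asks about day L, a day of use, so the answer is positive. The first entry that could qualify falls on L + 2, after exit. Without it the subject is censored, whatever the termination page says.

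**Step 3: illustrative size.** The documents give neither the share who stop for relief nor the share p of these without a qualifying entry. Assume first use on Day 1, 30% truly stopping for relief, a constant daily hazard h over Days 2 to 20 (19 days), and exit the day after last use for those without an entry.

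- (1 − h)^19 = 0.70, so h = 1 − 0.70^(1/19) = 0.0186.
- Of those still using the gel before day k, a share ph is censored on k, and (1 − p)h have the event at time k + 1. The hazard at that time is (1 − p)h / (1 − ph), and one minus this is (1 − h) / (1 − ph).
- Survival after 19 steps is 0.70 / (1 − ph)^19.

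| p | Survival | Day-21 estimate |
|---|---|---|
| 0% | 0.700 | 30.0% |
| 10% | 0.70 / 0.9653 = 0.725 | 27.5% |
| 25% | 0.70 / 0.9153 = 0.765 | 23.5% |

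At p = 0 only the date shift acts. True survival is 0.70^(15/19) = 0.755 at Day 16 and 0.70^(16/19) = 0.741 at Day 17, so the true first quartile is 17 days and the SAP reports 18. The Day-21 percentage is unchanged. At p = 25% the estimate stays below 25%, so the first quartile is not reached.

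**The case against.** **The report date may be intended.** First use is an act that happened the day before, so its shift is unavoidable. Relief is a state, and dating it when the subject first reports it is a defensible convention. The plus 1 is likewise the SAP's own counting rule. This stands in part. A reader might infer that every event time is simply wrong by a day, but the documents support that only if the diary entry date is meant and the SAP 7.1 convention is the standard. What remains is an unexplained mismatch between the two ends of one interval.

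**The protocol works against missed entries.** Section 8.1 asks subjects taken off treatment early to remain for the outstanding assessments. Section 9.2.2 has product use recorded in the eDiary each day, the end of use reported, and questionnaires completed before exit. Section 9.3 has the investigator review the diary at Days 7, 14 and 21. The diary also offers absence of pain as a reason for non-use, so such entries were expected. This stands as a reason to expect few missed events. It does not close the gap: the reasons listed in 8.1 do not include relief, and none of these sections requires an entry two days after last use.

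Taking section 9.2.3 literally for everyone, a reader might infer that no stop for relief could ever be recorded and the curve would stay at zero. The daily diary and the provisions above do not support that.

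**The effect is small.** A constant one-day shift in an untested exploratory estimate changes little. That is accepted.

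**Conclusion.** Both parts hold as minor points on an exploratory endpoint. If SAP 7.4.7.3 means the diary entry date, each diary-based event time is one day longer than under the convention of SAP 7.1, and the reported quantiles shift by about one day. Separately, the event rule censors a treated subject whose termination record says pain has gone but who has no qualifying diary entry, contrary to Protocol 13.3.4. Protocol 9.2.3 makes this possible; 8.1, 9.2.2 and 9.3 make it less likely. The number affected is unknown, and the figures of 27.5% and 23.5% rest wholly on the assumed shares and hazard.

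A reader might also infer that the endpoint as a whole is biased towards late and few events. That is not established, because a single pain-free skipped day counts as the event even if use resumes, which works the other way. Primary and secondary analyses are unaffected.

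**What to change.** 1. In SAP 7.4.7.3, set the event date to the diary date minus one day, as for first use, and require it to fall after first use. If the date of first report is intended, say so and explain why it differs from SAP 7.1.
2. For treated subjects with "Withdrawal due to no pain" and no diary event, count an event dated the day after "Date of last application of study drug", in the main derivation or as a labelled sensitivity analysis, and report how many there are. That date is L + 1 = k, so it matches item 1; if the report date is kept instead, the two kinds of event would sit one day apart and need aligning. This does not recover early stoppers recorded as completed or under another reason, so it should not be presented as a full correction.
3. Reconcile Protocol 8.1, 9.2.2 and 9.2.3 on what is collected after a subject stops using the gel.

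Items 1 and 2 cost a few derivation lines on data already in the eCRF and eDiary. A change made after the data review meeting should be labelled as such.

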##### 3.1.4 Exploratory Objectives

The exploratory objectives of the study are:

- To explore the link between Voltaren use, level of pain relief and functional mobility/quality of life.
- To evaluate time-to meaningful pain relief after Voltaren use.

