**Change from baseline in self-reported pain intensity, assessed through Numeric Rating Scale (NRS) (daily assessment).**

Self-reported pain intensity is recorded on the 'Numeric Rating Scale' eDiary page at each scheduled timepoint.

Baseline is the value collected on Day 0, as described in section 7.1.

Change from baseline is calculated as:

- NRS score at Scheduled Timepoint – NRS baseline score (Day 0)

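### The time-to-relief curve counts only pain-free non-use days, so it does not measure the named objective and only partly matches the protocol's stopping definition

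*SAP*

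**What the plan says.** Both documents name the objective in terms of relief. Protocol Table 3-1 has "To evaluate time-to meaningful pain relief after Voltaren Gel use" and SAP 3.1.4 has "To evaluate time-to meaningful pain relief after Voltaren use". Neither wording mentions stopping the gel.

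Protocol 13.3.4 describes the measurement differently, as the time from product use until relief is enough for the subject to stop using the product. The protocol synopsis differs again: it refers to Kaplan-Meier curves of QoL factors and a median time to symptom resolution.

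SAP 7.4.7.3 makes this operational: "Date of meaningful pain relief is defined as the earliest date where" both of two answers appear on the Study Product Use diary page. The first is *No* to "Did you use yesterday the Voltaren Gel as per label and leaflet instructions". The second, joined by AND, is that the reason given is *No pain anymore*. Anyone who finishes or leaves the trial with no such entry is treated as censored. For the timing, the SAP says that "the date of censoring is the date of study discontinuation recorded on the 'Study Termination' eCRF page".

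SAP 8.2.4 and 10.6.3 report the result as time to meaningful pain relief (events, censored, median with 95% CI, Q1, Q3), with no second definition or sensitivity analysis.

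Two other collected items do not enter the definition. For daily pain, SAP 7.4.7.2 states "Self-reported pain intensity is recorded on the 'Numeric Rating Scale' eDiary page at each scheduled timepoint". For termination, SAP 7.4.1 lists withdrawal due to no pain among the reasons.

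**The concern.** The reason question is reached only after a *No* on product use. A subject whose pain falls substantially, but who applies the gel as labelled every day to Day 21, answers *Yes* throughout and is censored with those who had no relief. Subjects are enrolled on their willingness to use the gel on label for up to three weeks, and stopping early is optional (Protocol 6.2, 9.2.2), so such subjects should be expected. The reason offered also appears to require that pain is gone, not that it is meaningfully reduced.

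At stake is what the reader takes from the table. A median titled time to meaningful pain relief would in fact describe when subjects first report not using the gel because they have no pain. Even as a stopping endpoint the rule is imperfect, since it looks at a single diary day and ignores the termination reason.

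**Working it through.** **No figure to reproduce.** The documents give no event rate, median or precision for this endpoint. The 147 completers come from a signed rank calculation unrelated to it; 147 is used below only to turn proportions into counts.

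**Step 1: who can be an event.** These four patterns test the rule against the objective and against Protocol 13.3.4.

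| Subject | Objective (meaningful relief) | Protocol 13.3.4 (relief enough to stop) | SAP 7.4.7.3 |
|---|---|---|---|
| Relief, keeps applying the gel daily | event | no event | censored |
| Pain gone, stops, diary entry made | event | event | event |
| Pain gone for a day, one non-use day, resumes | depends on definition | no event (has not stopped) | event |
| Terminates with withdrawal due to no pain, no matching diary entry | event | event | censored |

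Row 1 is the mismatch with the objective. Rows 3 and 4 are mismatches with 13.3.4, and they pull in opposite directions.

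Row 4 can occur in ordinary conduct. Protocol 9.2.3 ends the study the day after the last treatment if that is before Day 21. A diary entry on that day asks about the day before, when gel was used, so the answer is *Yes*. Read literally, such a subject is censored because the outcome occurred, which breaks the Kaplan-Meier assumption that censoring is unrelated to the event.

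**Step 2: size for the objective, simple form (all rates assumed).** Let R be the share with meaningful relief by Day 21 and q the share of those who also give the qualifying entry. With no earlier censoring, the recorded share by Day 21 is R × q.

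- R = 0.60, q = 0.25, 0.50, 0.75: 0.15, 0.30, 0.45. No median.
- R = 0.80, same q: 0.20, 0.40, 0.60. A median exists only in the last case.

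**Step 3: size with a time course (assumed).** Take exponential time to relief with median 10 days, 21 days of follow-up, and qualifying entries made at the time of relief. True share by Day 21 = 1 − 2^(−21/10) = 0.767, and 147 × 0.767 = 112.7 subjects. Recorded share by day t = q × (1 − 2^(−t/10)).

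| q | Recorded by Day 21 | Events of 147 | Curve at Day 21 | Median |
|---|---|---|---|---|
| 1.00 | 0.767 | 112.7 | 0.233 | 10 days |
| 0.75 | 0.575 | 84.5 | 0.425 | 10 × log2(3) = 15.8, about 16 days |
| 0.50 | 0.383 | 56.4 | 0.617 | not reached |
| 0.25 | 0.192 | 28.2 | 0.808 | not reached |
| 0.10 | 0.077 | 11.3 | 0.923 | not reached |

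A simulation under the same assumptions gave the same picture (about 84, 56, 28 and 11 events for q from 0.75 down to 0.10). Under this time course the median is lost once q falls below 0.5 / 0.767 = 0.65.

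**The case against.** The strongest reply is that the SAP does what the protocol asks. Protocol 13.3.4 ties the event to stopping, the synopsis speaks of symptom resolution, and the schedule footnote lets subjects stop once pain has resolved. Under that definition a subject who still chooses to apply gel has not had the event, and censoring that subject is correct. This stands: the non-use condition is the protocol's choice, not an SAP departure. What it does not rescue is the title, which promises meaningful relief, or the two places where the SAP rule differs from stopping.

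A reader might infer that relief in continuing users goes undetected in the trial. The documents do not support that. NRS change is modelled at Days 7, 14 and 21, WOMAC pain likewise, and over-time figures are planned. Only this curve cannot see it, though none of those analyses estimates time to relief.

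A reader might also conclude that a fixed percentage fall in NRS should replace the present definition. The documents contain no responder threshold. NRS baseline is a single Day 0 value, and Protocol 9.2.1 ends the baseline period on one qualifying VAS reading. With no control arm, natural fluctuation could register as early relief and make NRS times too short. That favours a supportive role for the NRS curve.

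Two further cautions stand. The other reasons on the diary page are not shown, so how a subject with partial relief would answer is uncertain. And SAP 2.0 already incorporates data review meeting updates, so a threshold chosen now comes late.

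**Conclusion.** The point holds as a mismatch between the endpoint's name and its measurement, plus an incomplete match to Protocol 13.3.4. For meaningful relief, the curve has too few events and a median that is too late or not reached whenever some relieved subjects keep using the gel. This takes a pain-free non-use day to be no earlier than the onset of meaningful relief. For stopping, the net direction of error cannot be determined, because single-day non-use adds events and unmatched withdrawals for no pain remove them.

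The size cannot be derived from the documents; every percentage in the working is an assumption, shown as a range. The endpoint is exploratory, descriptive and unconnected to the sample size, so primary and secondary results do not change. It is worth correcting because correction is cheap and the uncorrected table would report a median for something other than its title.

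**What to change.** 1. In SAP 7.4.7.3, 8.2.4 and 10.6.3, retitle the present curve as time to stopping gel because of no pain. Require that use is not resumed on later diary pages. Count withdrawal due to no pain on the Study Termination page as an event, and state how it is dated; the date of last application is on the same page.

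2. Add a supportive Kaplan-Meier curve from the daily NRS: first day with a fall from baseline of a size the sponsor chooses and justifies, held at the next recorded day, regardless of gel use. Label it post hoc if the threshold is set after database lock.

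Cost: SAP wording, a revised derivation, and one extra derived variable with its table and figure, all from data already collected. The downsides are the need to defend a threshold and the likelihood that natural fluctuation around a single Day 0 baseline shortens NRS times; the report should say so beside the curve. If only one change is made, the retitling matters most.

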### 9.2.3 End of Treatment Period/End Of Study

Subjects will have the option to discontinue treatment at their discretion. The reasons for discontinuing treatment will be captured whenever possible.

Subjects may choose to discontinue treatment if they feel that their symptoms do not warrant further use of the study product.

Subjects who wish to continue to use the study product will be prompted to discontinue treatment after the end of the study (28 days) and seek advice from their general practitioner for further assessment and treatment on their condition if needed.

Subjects will also be informed that the study will end on Day 21 (or the day after the last treatment, if earlier than 21 days), and will be asked to fill in an exit survey and perform final urine pregnancy test .

At the end of the study (Day 28), Actigraph device and the allocated product (used and unused) for this clinical study, should be returned to the Haleon Clinical Supplies Department or [CCI](#) using the return instructions provided.

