## Elapsed time from Voltaren Gel use to achieving time to meaningful pain relief to end of study

Time to meaningful pain relief is estimated using Kaplan-Meier method. This includes, patients with event, patients censored, time to meaningful pain relief (days), median with 95% confidence interval, Q1 and Q3. Time to event and censoring are derived as explained in section 7.4.7.3.

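### Time to meaningful pain relief: subjects who leave the study for lack of efficacy or an adverse event are censored like any others, which taken alone raises the Kaplan-Meier relief curve and makes its median and quartiles too early

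*SAP*

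**What the plan says.** SAP 7.4.7.3 defines the event from the Study Product Use diary alone. It is the earliest date on which the subject reports not having used the gel as per label the day before and gives absence of pain as the reason. Subjects who complete or discontinue without that entry are censored, and "the date of censoring is the date of study discontinuation recorded on the" Study Termination page. The rule does not depend on why the subject left.

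SAP 8.2.4 states: "Time to meaningful pain relief is estimated using Kaplan-Meier method". SAP 8.2.4 and 10.6.3 call for the numbers with event and censored, the median with its 95% confidence interval, Q1, Q3 and the curve, all in the mITT population.

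SAP 7.4.1 lists twelve possible reasons for discontinuation on the same Study Termination page. They include "Lack of efficacy", "Adverse Event (with a drop down to specify the AE number") and "Withdrawal due to no pain". None of them enters the censoring rule.

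Two protocol passages govern how long a subject who stops the gel stays under observation. Section 8.1 names adverse event and lack of efficacy as reasons to stop the intervention, and says the subject should remain and finish the assessments unless withdrawal is needed. Section 9.2.3 tells subjects that "the study will end on Day 21 (or the day after the last treatment, if earlier than 21 days").

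No estimand is defined (Protocol section 4), and no competing-risks or alternative censoring analysis is specified for this endpoint.

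**The concern.** Kaplan-Meier treats a censored subject as someone who would have gone on to relief at the same rate as those still observed. That is hard to defend for a subject who left because the gel did not work. A subject who left for that reason, or for an adverse event, can also no longer make the diary entry that defines the event. The observed relief rate of those who remain then stands in for them.

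At stake are the curve, the median and the quartiles. The protocol summary singles out the median for presentation, and a single-arm study has no comparator against which an inflated curve would show. In the worst case a median is reported although fewer than half of the subjects obtain relief within the treatment period.

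**Working it through.** **Inputs from the documents.** The treatment period is 21 days. Dropout is 25% from all causes (Protocol 13.1, SAP 3.2.1); 195 × 0.75 = 146.25 agrees with the stated 147 completers to rounding. The plan gives no figure for this endpoint, so there is none to reproduce.

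**Assumptions.** The documents do not give the true cumulative incidence of relief by Day 21 (F_r) or the share of the 25% that leaves the study for lack of efficacy or an adverse event. I vary both. Hazards are constant over 21 days, and no other early censoring is modelled.

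**Formulas.** With F_f = 0.25 × share:
- total cumulative hazard L = −ln(1 − F_r − F_f)
- relief hazard l = L × F_r / (F_r + F_f)
- Kaplan-Meier relief at Day 21 = 1 − exp(−l); the cumulative-incidence value is F_r
- Kaplan-Meier median = 21 × ln 2 / l

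**Worked case.** F_r = 0.40 and half of dropouts, so F_f = 0.125. L = −ln(0.475) = 0.744; l = 0.744 × 0.40/0.525 = 0.567; 1 − exp(−0.567) = 43.3%, against a true 40%.

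**Kaplan-Meier relief at Day 21, by share of dropouts leaving for these reasons:**

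| True relief | 25% share | 50% share | 100% share |
|---|---|---|---|
| 20% | 20.7% | 21.5% | 23.3% |
| 40% | 41.5% | 43.3% | 47.6% |
| 50% | 52.0% | 54.4% | 60.3% |
| 60% | 62.6% | 65.6% | 73.8% |

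**Quantiles.** With true relief of 50% the true median is Day 21.0; Kaplan-Meier gives 19.8, 18.6 and 15.8 for the three shares. With true relief of 40%, Kaplan-Meier puts Q1 at 11.3, 10.7 and 9.4 days, against 11.5, 11.2 and 10.4.

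**A median that should not exist.** Take true relief of 45% and the whole 25% leaving for these reasons: L = −ln(0.30) = 1.204; l = 1.204 × 0.45/0.70 = 0.774; Kaplan-Meier reads 53.9%, with a median at 21 × 0.693/0.774 = Day 18.8. At half the dropouts it reads 48.8% and no median falls within 21 days.

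**The opposing effect.** The diary asks about the previous day. If the gel is last used on day d, the entry on d+1 still reports use, and the first entry that could report non-use falls on d+2. Under Protocol 9.2.3 participation may already have ended on d+1. A subject who withdraws because the pain is gone may therefore never make the qualifying entry, and is censored. In a simulation (195 subjects, 400 runs, true relief 40%, 12.5% leaving for lack of efficacy or an adverse event), mean Day 21 Kaplan-Meier relief was 43.3% with no missed entries, 39.6% with 10% of relief entries missed and 36.0% with 20% missed.

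**The case against.** The strongest reply has five parts.

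*Subjects who stop the gel need not leave.* A reader might infer that everyone who stops for lack of efficacy or an adverse event is dropped from the risk set the next day. The documents do not support that. Censoring is at study discontinuation, and Protocol 8.1 keeps exactly these subjects in the study; those who stay remain at risk without the event and cause no bias. Protocol 9.2.3 points the other way. The conflict stands, and the point is confined to subjects who actually leave.

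*The net bias may not favour the product.* A reader might infer that it always does. The censoring of no-pain withdrawals without a diary entry works in the other direction and can cancel or reverse it, as the simulation shows. This stands.

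*The larger figures are extremes.* The 25% covers all reasons. Protocol 9.2.2 also counts subjects who never use the gel as dropouts, and they are outside the mITT population and so outside this curve. This stands; the 100% column is a bound and not a forecast.

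*The number with relief is shown anyway.* The table reports the crude counts with event and censored, which this rule does not inflate. This is correct. The curve, median and quartiles are what shift.

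*The endpoint is exploratory.* No test or sample size rests on it. This is also correct, and it limits the weight of the point.

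The reply does not rescue the rule itself. One could say that Kaplan-Meier targets relief had nobody left, but the plan defines no such estimand, and censoring for lack of efficacy would then have to be unrelated to prognosis. The SAP's general provision leaves further sensitivity analyses to data review; version 2.0 already incorporates the data review updates and specifies none for this endpoint.

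**Conclusion.** The point holds for the censoring rule taken alone. Whenever subjects leave the study for lack of efficacy or an adverse event, and these exits are counted as failures to obtain relief, one minus Kaplan-Meier is at or above the true cumulative incidence and its quantiles are at or before the true ones.

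The size depends on assumptions that the documents do not settle. The Day 21 excess is about 1 to 3 points if a quarter of dropouts leave for these reasons and true relief is 20 to 60%. It is 8 to 14 points if all do and true relief is 40 to 60%, where the median can be up to about 5 days early or be reported when fewer than half obtain relief. All of this assumes constant hazards.

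The net direction of the reported curve is not established, because no-pain withdrawals without a matching diary entry are censored too. The primary conclusion and the crude count of diary-defined events under the current rule are unaffected. This is a cheap improvement to an exploratory analysis.

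**What to change.** In SAP 7.4.7.3 and 8.2.4, make the analysis depend on the Study Termination reason:

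- Treat study discontinuation for lack of efficacy or an adverse event as a competing event. Report the cumulative incidence of relief (Aalen-Johansen), with a median only if the curve reaches 50%.
- Count withdrawal for absence of pain as the relief event, and state which recorded date applies. Correcting only the competing exits would remove the upward component and leave the downward one.
- Censor at completion, loss to follow-up or withdrawal for unrelated reasons, and assign each of the twelve listed reasons to a category.
- Keep the current Kaplan-Meier analysis as sensitivity.

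Holding the failures event-free to Day 21 is not a general substitute: it matches the cumulative incidence only when there is no other early censoring.

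Protocol 8.1 and 9.2.3 must be reconciled on whether a subject who stops the gel stays under observation, since this decides who is censored early.

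The reasons are already collected, so the cost is SAP wording, a little more analysis work and a possibly less favourable curve. The event count will rise where no-pain withdrawals are added.
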